7.4.5.2.1 Diabetes management

Last injection or bolus administration via continuous SC insulin infusion of any insulin medication should not take place within the 12 hours before dosing. Patients normally using insulin aspart will be switched to human soluble insulin or glulisine for the period between 12 and 10 hours prior to dosing, if needed. Patients using continuous SC insulin infusion will have their pump switched off at 22:00 hours.

To achieve a target glucose level of 90-160 mg/dL (5.0-8.9 mmol/L) in the morning of dosing, patients may be administered insulin glulisine and/or glucose at the discretion of the investigator by IV infusion using the following glucose infusion rate and insulin infusion rate as a guidance. Deviation from the guidance is allowed at the discretion of the investigator. Plasma glucose levels will be checked overnight at regular intervals in order to achieve and maintain the target plasma glucose level of 90-160 mg/dL (5.0-8.9 mmol/L).

A general guidance for administration of insulin IV and/or glucose IV at the dosing visit

Fluid infusion rate:

If plasma glucose < 300 mg/dL, then infusion of isotonic solution with 5% glucose:

Age 6–10 years: 80 mL/kg/24 h

Age >10 years: 60 mL/kg/24 h

If plasma glucose >300 mg/dL the glucose infusion will be substituted with fluid volume of normal saline (0.9% NaCl) at same infusion rate as above.

Insufion of insulin:

Insulin infusions should be performed with 0.5 IU insulin glulisine (Apidra®) per kg body weight in 48 mL NaCl 0.9% according to the following recommendations:

Glucose	Infusion rate	Insulin dose (IU/kg BW/h)
>200 mg/dL	10.0 mL/h	0.1
150–200 mg/dL	5.0 mL/h	0.05
80-150 mg/dL	2.5 mL/h	0.025
<80 mg/dL	Insulin infusion stop!	0

Abbreviation: BW=Body weight

7.4.5.2.2 Hypoglycemic clamp procedure and dosing

At the time of admission to the clinic, which is the day before clamp procedure, the patient's eligibility must be checked. If the patient meets any of the exclusion criteria at the time of admission to the clinic at V2, he/she will be excluded from the dosing visit but may be rescheduled once 1-7 days later.

Eligible patients will be randomized to either dasiglucagon, placebo or GlucaGen® in the morning of the dosing visit. That morning after 7 o'clock am, the infusion of IV glucose will be stopped. This should be at least 30 minutes prior to planned trial product administration. Insulin infusion rate and insulin dose are at the discretion of the investigator or can follow the protocol general guidance (see above). The investigator may deviate from the guidance. Insulin IV infusion will be stopped when glucose level declines to below 80 mg/dL.

During insulin-induced hypoglycemia, plasma glucose levels will be monitored closely at the site. After the start of insulin infusion, plasma glucose should be checked approximately every 10 minutes while plasma glucose is above 110 mg/dL, approximately every 5 minutes once plasma glucose is at or below 110 mg/dL, until after dosing, when the patient's plasma glucose returns to ≥ 70 mg/dL (3.9 mmol/L). From that time on, plasma glucose should be checked approximately every 30 minutes until 300 minutes (5 hours) after dosing. Plasma glucose concentrations will be measured using the US FDA-approved glucose analyzer YSI 2300, Yellow Springs Instruments,

Yellow Springs, Ohio, USA or the Super GL analyzer, [name] GmbH, Freital, Germany.

At the discretion of the investigator, additional plasma glucose measurements can be taken at any time during the trial, for example when there is a suspicion (e.g. symptoms) of a hypoglycemic episode.

Plasma glucose measurements for safety should only be recorded in the eCRF if they are related to an AE (e.g. a hypoglycemic episode).

In case of persistent post-treatment hypoglycemia, patients will receive rescue treatment with an IV glucose infusion (see [Section 7.4.5.2.3](#) for details). Blood samples for PD and PK assessments should still be taken at the specified time points.

Once the glucose concentration declines to <80 mg/dL, blood samples for baseline assessment of plasma glucose and dasiglucagon/GlucaGen PK will be collected 5 minutes later. The samples are the baseline samples and should be collected within 2-5 minutes before trial product administration. If plasma glucose is ≥ 54 mg/dL and <80 mg/dL (3.0-4.4 mmol/L), trial product will be administered.

If plasma glucose is <54 mg/dL (3.0 mmol/L), IV glucose solution will be administered sufficient to raise plasma glucose to within the 54-80 mg/dL target range. The run-in period will be adequately extended (at least 30 minutes) until the above target is achieved and new baseline samples for plasma glucose, dasiglucagon/GlucaGen PK, will be collected. In this case, glucose should not be infused within 10 minutes before trial product administration. If plasma glucose is not within the target range after the second attempt, the patient should be rescheduled for a new treatment visit within 7 days (+ 2 days).

After 60 minutes, patients will be allowed to eat and drink moderately (appropriate to their body size, with a maximum of 50gr carbohydrates) to minimize discomfort in terms of potential nausea. The amount and type of food and drink consumed will be recorded. Patients should remain in bed until completion of the test procedure 300 minutes after dosing (bathroom visits are allowed).

7.4.5.2.3 Rescue provisions for hypoglycemia

During insulin-induced hypoglycemia, plasma glucose levels as well as the patient status will be monitored closely throughout the procedure. After administration of trial product, if their glucose levels become too low, patients may receive post-treatment IV glucose infusion to ameliorate hypoglycemia, as follows:

1. The IV glucose infusion should be initiated if a patient experiences escalating symptoms of hypoglycemia (e.g. start of moderate symptoms of hypoglycemia) at any time during the test procedure. Glucose infusion should then be initiated targeting a plasma glucose level >70 mg/dL
2. If plasma glucose is <54 mg/dL between t=8 and t=44 minutes, glucose infusion (e.g. 1-2 mg/kg administered over 5-10 seconds) should be initiated to maintain plasma glucose between 55 mg/dL and 70 mg/dL. Pause glucose infusion if plasma glucose is >70 mg/dL
3. If plasma glucose is <70 mg/dL at $t \geq 45$ minutes, glucose infusion (e.g. 2-3 mg/kg administered over 5-10 seconds) should be initiated to maintain plasma glucose between 70 mg/dL and 90 mg/dL. Pause glucose infusion if plasma glucose is >80 mg/dL

7.4.6 Selection of doses in the trial

The selected dose of 1 mg GlucaGen® is the recommended dose for treatment of severe hypoglycemia (in accordance with the label, children below 25 kg body weight will be administered 0.5 mg GlucaGen®). Pre-clinical and adult clinical studies demonstrated that 0.6 mg of dasiglucagon results in an initial PD response (i.e. acute glucose mobilization) comparable to 1 mg GlucaGen®.

The estimation of the dasiglucagon dose in the pediatric trial is based on a PK and PD approach⁶ where a previously developed population PK/PD model³ for dasiglucagon was extended with an allometric scaling component for the PK model⁴. The PD response was assumed to be similar in pediatric and adult patients as organ maturation for patients above 4 years is assumed not to have a meaningful impact on dasiglucagon PD. The pediatric PK component was developed by allometric scaling of clearance (Cl) and volume (V) by body weight from published glucagon PK data obtained from 2 clinical trials following intramuscular administration to pediatric (4 to 17 years) and adult T1DM patients^{11,9}.

The conclusion of the modelling was that a dose of 0.6 mg appears appropriate to ensure a fast rescue from hypoglycemia for adult patients and children down to a weight of 25 kg. Although the dasiglucagon C_{max} and AUC is expected to be higher in children, it does not exceed the total C_{max} and AUC obtained in adults previously administered 2 mg dasiglucagon. The higher total drug exposure (AUC and C_{max}) at lower weight is partially compensated by the shorter t_{1/2} and saturated PD response. The resulting total time of drug exposure and PD effect (AEU and CE_{max}) is similar throughout the weight range.

7.4.7 Collection of blood samples

The total blood volume to be obtained from any individual child will be about 43 mL. The maximum amount per visit is 12 to 17 mL. These values are within the recommended scope provided by the EU⁵.

The following blood volume will be taken for each sample at each visit:

Sample type	Visit 1 (mL)	Visit 2 (mL)	Visit 3 (mL)
Biochemistry/pregnancy	5.00	-	5.00
Hematology	2.00	-	2.00
Coagulation	2.00	-	2.00
HbA1c	2.00	-	-
ADA	3.00	-	3.00
PK	-	4.00	-
PD	-	12.00	-
Onsite-PG	-	1.00	-
Sum for each visit	14.00	17.00	12.00
Total	43.00		

Abbreviations: ADA=Anti-drug antibodies; HbA1c=Hemoglobin A1c; Onsite-PG=Onsite monitoring of plasma glucose; PD=Pharmacodynamics; PK=Pharmacokinetics

7.4.8 Treatment compliance

Unblinded trial personnel will handle, prepare and administer all trial products.

7.4.9 Method of assigning patients to treatments

Forty patients will be randomized in a 2:1:1 ratio (dasiglucagon/placebo/GlucaGen®) into the 3 treatment arms and stratified in 2 age groups: 6 to ≤12 years and 12 to ≤18 years and by injection site (abdomen/thigh). A minimum of 16 patients will be enrolled into each age group, including a minimum of 8 patients in either of age groups on dasiglucagon treatment arm.

Patients who meet the inclusion and exclusion criteria will be randomized into one of the following treatment arms:

- Dasiglucagon, liquid formulation, 1 mg/mL, 0.6 mL

- Placebo treatment: Placebo, liquid formulation, 0.6 mL
- Active control treatment: Recombinant glucagon hydrochloride, 1 mg lyophilized powder for reconstitution (GlucaGen[®], Novo Nordisk) in 1 mL sterile water (in accordance with the label, children below 25 kg body weight will be administered 0.5 mg GlucaGen[®])

Randomization will be performed using a central, dynamic variance minimization randomization method using an interactive web response system (IWRS) that will randomize a patient to one of the 3 aforementioned treatment arms and then assign dispensing unit numbers to that patient.

An unblinded statistician/programmer who is separate from the trial team will generate the randomized kit list before the initiation of the trial.

Treatment assignment will be kept strictly confidential and accessible only to authorized persons until after data base lock. However, the investigators can perform an emergency unblinding within the IWRS in case of an emergency, see [Section 7.4.10](#).

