10.1.3.2 Primary efficacy endpoint

The primary endpoint, time to plasma glucose recovery, will be summarized using Kaplan-Meier estimates for each treatment group in total and stratified by age group and injection site. The median time to recovery with 95% confidence interval will be estimated by treatment group, in total and in each stratum.

A stratified log-rank test will be applied to compare the dasiglucagon 0.6 mg treatment group to the placebo group. The same method will be applied to compare dasiglucagon 0.6 mg with GlucaGen®.

In the primary analysis, recovery cannot be achieved in those patients where IV glucose treatment is administered. Those patients who receive IV glucose will be censored (i.e. set to 'not recovered') at 45 minutes after dosing.

A further sensitivity analysis will be done by censoring data at the actual time when the patients received glucose IV.

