10.2 Determination of sample size

The primary comparison is between the dasiglucagon and placebo treatment arms. From phase 2 results, the median time to an increase of 20 mg/dL of the 0.6 mg dose was approximately 10 minutes. For placebo-treated patients, the median time to recovery is assumed to be more than 50 minutes. Assuming an exponential time-to-recovery distribution with median times of 10 and 50 minutes, a 2-sided log-rank test will be able to detect a difference between dasiglucagon 0.6 mg and placebo with 90% power with a follow-up time of 45 minutes at a 5% significance level with 20 patients randomized to the dasiglucagon arm and 10 patients to placebo.

GlucaGen[®] is included as a reference to compare the responses and AE profile to dasiglucagon with those to a marketed product. It is expected that 10 patients in the GlucaGen[®] group will suffice for the comparison.

11. Ethics and regulations

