## 5. DETERMINATION OF SAMPLE SIZE

The primary comparison is between the dasiglucagon and placebo treatment arms. From phase 2 results, the median time to an increase of 20 mg/dL of the 0.6 mg dose was approximately 10 minutes. For placebo-treated patients, the median time to recovery is assumed to be more than 50 minutes. Assuming an exponential time-to-recovery distribution with median times of 10 and 50 minutes, a 2-sided log-rank test will be able to detect a difference between dasiglucagon 0.6 mg

and placebo with 90% power with a follow-up time of 45 minutes at a 5% significance level with 20 patients randomized to the dasiglucagon arm and 10 patients to placebo.

GlucaGen® is included as a reference to compare the responses and AE profile to dasiglucagon with those to a marketed product. It is expected that 10 patients in the GlucaGen® group will suffice for the comparison.

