## 11. METHODS OF EFFICACY ANALYSIS

### 11.1 Primary Efficacy Analyses

The primary endpoint, time to plasma glucose recovery, will be summarized using Kaplan-Meier estimates per treatment group.

The actual time points at 0, 4, 6, 8, 10, 12, 15, 17, 20, 30, 45 and 60 minutes will be used in the analyses.

Kaplan-Meier plots will be created showing the the estimated survival function for each treatment in one plot.

In the primary analysis, recovery cannot be achieved in those subjects where rescue IV glucose treatment is administered. Those subjects who receive rescue IV glucose will be censored (and set to 'not recovered') at 45 minutes after dosing.

For patients who did not recover within 45 minutes after dosing, time to recovery is censored at 45 minutes.

The stratified log-rank test will be applied to compare the dasiglucagon 0.6 mg treatment group to the placebo group. The same method will be applied to compare dasiglucagon 0.6 mg with GlucaGen®, but not considered for the confirmatory hierarchical testing procedure.

In order to facilitate this, SAS procedure proc lifetest is used. The following code will be used, but minor variations can be applied during programming:

```
proc lifetest data=xx plots=survival(atrisk=0 10 15 20 30 45);  
  time aval * Status(0);  
  strata age site/ group= treat test=logrank diff=all;  
run;
```

where "aval" is the time to plasma recovery, and "status" is a censor variable for patients who receive IV glucose. Age group and injection site are the stratification variables and "treat" the planned treatment assignment.

The unstratified result of the log-rank test can be obtained from the following code:

```
proc lifetest data=xx plots=survival(atrisk=0 10 15 20 30 45);  
  time aval * Status(0);  
  strata treat / test=logrank diff=all;  
run;
```

In sensitivity analyses, the time to plasma glucose recovery will be analyzed

- 1) without censoring for those subjects who require rescue IV glucose before 45 minutes and
- 2) with censoring at the time of administration of rescue IV glucose before 45 minutes.

As a supportive analysis to the stratified log-rank test for the time to plasma glucose recovery, dasiglucagon will be compared to placebo using a Wilcoxon test stratified by age group and injection site.

To graphically describe recovery in time, a histogram showing the proportion of patients that recovered at each time interval will be created, one for each treatment group.

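### The stated 90% power belongs to an unstratified log-rank test; the primary test, stratified over four age-by-site cells, has about 87–88% under the same inputs

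*Protocol*

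**What the plan says.** Power. Protocol 10.2 states that "a 2-sided log-rank test will be able to detect a difference between dasiglucagon 0.6 mg and placebo". The power claimed is 90%, for 45 minutes of observation and a 5% level. The inputs are 20 children on dasiglucagon, 10 on placebo, and exponential recovery times with medians of 10 and 50 minutes. The same section assumes that the true placebo median lies above 50 minutes. The synopsis has the same text, and SAP 5 repeats it ("and placebo with 90% power with a follow-up time of 45 minutes"). None of the three mentions stratification.

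Primary test. Protocol 10.1.3.2: "A stratified log-rank test will be applied to compare the dasiglucagon 0.6 mg treatment group to the placebo group". SAP 11.1 says the same and codes it as "strata age site/ group= treat test=logrank diff=all", which crosses two age groups with two injection sites. SAP 11.1 also gives code for an unstratified result, but as an extra output. The list of changes in SAP 15 does not mention the sample size.

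Allocation. Protocol 7.4.9 allocates 40 children 2:1:1, stratified by age group and injection site, and continues: "Randomization will be performed using a central, dynamic variance minimization randomization method using an interactive web response system (IWRS". It does not give the minimization factors, their weights or the random element, and it does not say whether margins or cells are balanced.

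**The concern.** The test that was powered is not the test that decides the trial. A stratified log-rank test compares children only within their own age-by-site cell. With 10 placebo children over four cells there are about 2.5 per cell. Risk sets are small, and once a cell has only one arm left at risk, its later recoveries contribute nothing. A cell without any placebo child drops out of the primary comparison altogether. With non-prognostic strata, which the plan's single exponential per arm implies, nothing offsets this loss.

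The stake is whether the power figure describes the confirmatory analysis. That analysis opens the hierarchy in Protocol 10.1.3.1 and SAP 10.7, in a trial where dosed children are not replaced.

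**Working it through.** **Inputs from the plan.** Two-sided 5% level; 20 v 10 children; exponential medians 10 and 50 minutes (hazard ratio 5); censoring at 45 minutes; no dropout in the sample-size text.

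**Expected events.** P(recovery by 45 min) = 1 − 2^(−45/10) = 0.956 on dasiglucagon and 1 − 2^(−45/50) = 0.464 on placebo. Events = 20 × 0.956 + 10 × 0.464 = 23.8.

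**Reproducing the 90%.** Let φ(t) be the ratio of children at risk (dasiglucagon to placebo) and D(t) the expected events at time t. Then the mean of the unstratified log-rank Z is

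Σ D·[5φ/(1+5φ) − φ/(1+φ)] / √(Σ D·φ/(1+φ)²) = 7.564 / √5.438 = 3.244,

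and power = Φ(3.244 − 1.960) = 90.0%. The stated figure is therefore correct for the unstratified test.

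**The planned test.** It has no simple closed form here, so it was simulated with 20,000 to 100,000 trials per setting (Monte Carlo standard error 0.1 to 0.3 points). Assumptions that the documents do not give: 20 children per age group, the two sites used equally, strata not prognostic. Minimization is of the Pocock–Simon variance type, with preferred-arm probability 0.9 on margins and 0.95 on cells. All figures are for a test on the two arms alone; how the SAS step forms its pairwise contrasts is a separate question.

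| Test and allocation | Continuous times | Protocol glucose times |
|---|---|---|
| Unstratified | 92.5% | 92.5% |
| Stratified by age only, minimization on margins | 91.1% | 91.5% |
| Four cells, balanced by design | 87.9% | 89.0% |
| Four cells, minimization on cells | 87.3% | 88.7% |
| Four cells, minimization on margins | 86.6% | 87.6% |
| Four cells, left to chance | 85.0% | 85.7% |

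With margin minimization on continuous times the result stays between 86.6% and 87.1% for preferred-arm probabilities from 0.8 to 1.0.

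**Where the loss arises.** On continuous times, stratifying over perfectly balanced cells costs 92.5 − 87.9 = 4.6 points, and margin minimization a further 87.9 − 86.6 = 1.3. On the glucose sampling times the two steps are 3.5 and 1.4 points. Margins against cells differ by 0.7 and 1.1 points.

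**Empty cells.** A cell has no placebo child in about 5% of trials under margin minimization, 0.3% under cell minimization and 19% when left to chance.

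**Placebo median.** With margin minimization and continuous times, the four-cell test has 92.0% at 60 minutes, 95.8% at 75 and 98.2% at 100. At 60 minutes on the glucose sampling times it has 93–94%.

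**Type I error.** The four-cell test rejects in 5.3–5.6% of trials with equal medians of 10, 20 or 50 minutes.

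**The case against.** The 90% is not a miscalculation; it is right for the test that it names. There are also good reasons to expect more power than 87% in practice. The plan treats 50 minutes as a lower bound for placebo. The rescue rule sets any rescued child to not recovered at 45 minutes; this should fall mainly on placebo, because rescue is triggered by low glucose or symptoms, and it would widen the contrast. Protocol 5.1 reports that every phase 2 patient rose by 20 mg/dL within 30 minutes, whereas an exponential with median 10 leaves 2^(−30/10) = 12.5% unrecovered by then. With an assumed Weibull shape of 2 and the same medians, the four-cell test has 96.8%. All of this stands as evidence that the trial is not underpowered. It does not rescue the figure, because the 90% is attached expressly to medians of 10 and 50 minutes.

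A reader might infer that the fault lies in the randomization: that minimization balances age and site separately and so starves the analysed cells. The documents do not say that it does. Even if it did, the effect is about 1 point, and perfectly balanced cells would still leave the test at 88–89%.

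It is also fair to say that any replacement figure depends on unstated allocation settings and on the assumed site split. That is a reason to state them, not to keep a figure for another test.

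**Conclusion.** The mismatch is real and small. At the plan's own inputs the stratified primary test has about 87–88% power (85–89% over the allocations and observation schemes tried). That is 2–3 points below the stated 90%, and about 4–6 points below the unstratified test simulated alike. Most of the loss comes from splitting 30 children over four strata.

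It is tempting to read this as a 13% chance of missing the effect instead of 10%. That holds only at a placebo median of exactly 50 minutes with exponential times. The plan expects a longer placebo median, and by 60 minutes the power is above 90% again. No case for more patients follows, and type I error stays close to 5%. The result rests on non-prognostic strata, equal use of the two sites and equal age groups.

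**What to change.** In Protocol 10.2, the synopsis and SAP 5, name the log-rank test stratified by age group and injection site. Restate its power as about 87% at medians of 10 and 50 minutes, with the allocation assumption beside it. A clause giving about 92% at a placebo median of 60 minutes would put the figure in context. This costs one sentence in three places and a slightly less favourable number; the test and the sample size stay as they are.

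In 7.4.9, say whether minimization uses the factor margins or the cells. Optionally, include the age-by-site cell as a minimization factor. This is one setting in the randomization system. It cuts trials with a cell lacking any placebo child from about 5% to under 1% and adds at most 1–2 points of power, so it does not by itself bring the test to 90%.

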7.4.10 Blinding and breaking the blind

This is a double-blind trial. Dasiglucagon is available as a liquid formulation and GlucaGen[®] is available as a powder for reconstitution; they are therefore not identical in appearance. Unblinded trial personnel will be responsible for handling, preparing (according to the prescription from the IWRS), and administering the trial product, and the syringes used for administration will be wrapped in aluminum foil to maintain the blinding at bedside. Parents being in the room with their child must be instructed not to look while the unblinded staff is administering the injection. To maintain double-blind conditions, blinded trial personnel not involved in the administration of trial products will perform all trial assessments at the trial center and is responsible for keeping the records strictly confidential and accessible only to the unblinded staff. However, unblinded personnel at the specialty laboratories will perform the exposure assessments and ADA assessments to make sure that dasiglucagon or GlucaGen[®] administration is matched with the applicable bioanalytical assay.

Treatment assignment will be kept strictly confidential and accessible only to authorized persons until after the time of unblinding (database lock). Codes with treatment assignment will however be readily available in the IWRS to the blinded personnel in case of an emergency.

The code for a particular patient may be broken in a medical emergency if knowing the identity of the treatment allocation would influence the treatment of the patient. The emergency code break can be performed using the IWRS. Whenever a code is broken, the person breaking the code must record the time, date and reason as well as his/her initials in the source documents.

The breaking of blinded codes in case of medical emergency for a patient should not unblind the trial personnel to the treatment information of other patients. The person performing the unblinding should inform as few people as possible about the result of the unblinding. All persons unblinded for a specific patient should be documented.

If the trial center needs to break the code, the medical monitor should, if at all possible, be contacted prior to breaking the code and the monitor must be notified within 24 hours after the code has been broken.

